For those who are deemed eligible for the study after the in-person screen, they will also complete the baseline survey (can be sent via email), where they will answer questions on demographics, drinking history, alcohol use disorder, alcohol effects, drinking motives, other substance use, and HIV treatment/adherence (for HIV+ participants only). Information obtained from these questions will be used to explore factors contributing to interpersonal variations in transdermal alcohol concentration and how they impact participant compliance in the field test (as some preliminary findings for building a larger project on this exploratory R21).

Lab Session 1. Participants will be asked not to eat for 3 hours pre-arrival, and arrive with a non-positive BrAC reading (.00%) detected by a laboratory degree breathalyzer (Alco-Sensor VXL, Intoximeters). In the event that an individual registers a positive breath alcohol level, there will be two possibilities. If the individual's breath alcohol level is likely to decline to 0.00% in a reasonable amount of time (i.e., 0.02% or lower), they will be offered the chance to remain at the research facility to be re-tested and take part in the appointment when their breath alcohol level reaches 0.00%. If it is not feasible for the participant to wait, they will be offered one opportunity to reschedule this appointment. Instruction/practice of the EMA app, Skyn monitor and its app will take place prior to the drinking session when participants are sober. The RA will help participants download the EMA app (Sec.4.4) on their smartphone, enter an 8-digit unique ID code for each participant, and show them how to enter a drinking session and answer the prompted questions. The RA will also help download the Skyn app and show participants how to pair the app with the monitor. The recording of data should automatically begin once the Skyn monitor is paired with the app. Instructions and demonstration of how to charge and operate the Skyn monitor will also be given. Procedures for the two-week field test will be explained. Participants will have time to

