practice with the apps and monitor until they feel efficient with all. Further, participants may also be asked to wear the Secure Continuous Remote Alcohol Monitor (SCRAM; Alcohol Monitoring Systems, Inc.) anklet for the duration of the drinking session. The SCRAM anklet is similar to the Skyn device although it is worn around the ankle rather than the wrist. The SCRAM anklet will be used to evaluate whether transdermal alcohol concentration (TAC) readings obtained from each device converge, given that the SCRAM anklet is a validated TAC monitor. The SCRAM anklet has been approved and risk assessed in our previous study ([IRB201700623](#)).

Once practice with apps and monitor is completed, vital signs (including blood pressure, pulse, height and weight) will be collected, urine drug and pregnancy screening will occur, and participants will be provided a light snack (150-200 calories). Next, participants will be asked to complete some questionnaires (e.g., Alcohol Urge Questionnaire (AUQ); Positive and Negative Affect Scale (PANAS); Alcohol Purchase Task (APT); real time impaired control scale (ICRT); and a single-item question asking how much one wants alcohol currently).

Next, the drinking session will begin. We will provide several common beer brands with similar calorie (125-150) and alcohol level (~4.5% ABV) for the participants to choose from. Participants will be instructed to wear the Skyn monitor and SCRAM anklet and drink 3 beers by completing each beer in 15 minutes⁵⁰ with a 15-minute break in between (30min in total for each beer). During this time, the participant's BrAC will be measured every 30 minutes. Following the end of each beer during the 15-minute rest period, participants will also complete a brief packet of questionnaires very similar to the one they completed before drinking, plus the Biphasic Alcohol Effects Scale (BAES) and a single-item question asking how much one likes the effects of alcohol. Alcohol administration will be conducted per NIAAA guidelines⁵¹.

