EMA: Participants will be instructed to enter information on each drinking session using an EMA app called mEMA (ilumivu, Inc.). This app is developed for mobile-based ecological momentary assessment to collect real-time data in daily life (Fig. 4). Researchers can create questions and set up the prompt type for each question (e.g., scheduled, or on-demand). In this study, participants will be asked to initiate an on-demand survey in the app whenever they start a drinking episode. This survey include questions regarding the drinking episode such as the starting and ending times of each drink, types of drinks, drinking amount, and food intake. To capture any potentially missed self-initiated entry at the time of drinking, the EMA app will also prompt questions at a fixed schedule every morning to ask about alcohol consumption in the past 24 hours. The morning prompts will also include reminders to check the battery life of the monitor and to upload EMA data, and report issues they had with the Skyn monitor. The app uses cloud storage and researchers can access data in real time once uploaded by the participants. We will contact participants via phone call if we notice any issues (e.g., missing daily prompt, reported monitor malfunction) so that these issues can be resolved in time. Participants will receive \$70 (\$5/day) and a bonus of \$70 if they complete ≥80% of the EMA questions, wear the monitor ≥80% of the time, and return it to the lab.⁵²

Lab Session 2. For those who are asked to complete all study components, after completing the two-week field test, participants will return to the lab for a second drinking session. The procedures will be the same as in Lab Session 1 with only one exception: Instead of training/practice with the monitor and app, participants will be asked to complete a survey on the acceptability and usability of Skyn and its app. The survey will include questions adapted from established instruments such as the System Usability Scale⁵³ and the Mobile App Rating Scale⁵⁴, with some open-ended questions about user-desired features. Before dismissal, the RA will help uninstall the apps on the participant's phone. Payment structure is the same as in Lab Session 1.

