Analysis plan for Aim 1: *Assess the validity and reliability of the Skyn monitor through comparison with laboratory grade breathalyzer in two fixed-dose lab alcohol administration sessions.* H1a. Threshold of detection. We define the threshold of detection as the consumption level with a 60% or higher detection rate. Rate of successful detection at the end of 1 beer, 2 beers, and 3 beers will be calculated respectively. This will be done by observing the data series and curves from the monitor readings.^{45,48} Successful detection of consumed alcohol is defined by a TAC peak (e.g., $\geq 0.02\text{g/dL}$) with a reasonably visible elevation slope for absorption (i.e., TAC curve goes up at a reasonable pace) and a declination slope for elimination (i.e., TAC curve goes down at the reasonable pace). H1b1. Relationship between TAC and number of drinks. The means of peak TAC readings and the areas under the curve will be calculated for 1, 2, and 3 drinks respectively. We expect a linear increase of peak TAC and area under the curve as number of drinks increase from 1 to 3. H1b2. Relationship between TAC and BrAC. We will examine the relationship between TAC and BrAC in three ways. First, a simple correlation will be calculated between recorded peak TAC and peak BrAC. A scatter plot will be produced to illustrate the bivariate correlation between these two readings. Second, the Bland-Altman method^{55,56} will be used to examine the magnitude of peak differences between TAC and BrAC. The average of paired TAC and BrAC peak values are plotted on x-axis, and the difference between them on y-axis. Stable TAC results across all BrAC levels will line up with a zero slope, which will suggest there is no systematic bias in estimating BrAC. Third, we will calculate the time-to-peak based on recorded TAC and BrAC readings. Their differences will be calculated to determine time delays in BrAC to TAC peaks. All these analyses will be conducted for TAC and BrAC readings obtained after each beer respectively. H1c: Two-week test-retest reliability. Pearson correlational coefficients will be calculated to indicate test-retest reliability using TAC peak /time-to-peak for each participant in two lab sessions. A correlation $\geq .7$ indicates good test-retest reliability.

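### Lab sessions are cleared for alcohol by breath alone and TAC has no pre-drink baseline, so residual TAC from recent drinking can enter the TAC measures but not BrAC

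*Combined protocol and SAP*

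**What the plan says.** Section 6 (Lab Session 1) of the combined protocol and SAP asks participants to "arrive with a non-positive BrAC reading (.00%) detected by a laboratory degree breathalyzer". Someone at 0.02% or lower may stay on site and "take part in the appointment when their breath alcohol level reaches 0.00" percent; if waiting is not feasible, one rescheduling is offered. The only abstention stated for the hours before arrival concerns food: "Participants will be asked not to eat for 3 hours pre-arrival". No alcohol-free interval and no TAC condition is given. For Lab Session 2, "The procedures will be the same as in Lab Session 1 with only one exception": a usability survey replaces device training.

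On the device, "The recording of data should automatically begin once the Skyn monitor is paired with the app", and pairing takes place during practice, ahead of the beers. The instruction to wear the monitor, however, appears only where the drinking period begins. No use of pre-drink readings is described.

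The analysis plan for Aim 1 expects TAC to run behind BrAC: "Their differences will be calculated to determine time delays in BrAC to TAC peaks". H1b1 uses mean peak TAC and AUC for one, two and three drinks. H1a counts alcohol as detected when TAC shows a peak (0.02 g/dL is the example) with a visible rise and a visible fall. H1b2 compares TAC and BrAC peaks after each beer. H1c correlates TAC peak and time-to-peak between the two sessions. None of these is referred to a starting value.

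**The concern.** The entry check tests the comparator, not the device being validated. If TAC trails BrAC, a breath reading of zero does not show that TAC is zero. The situation is foreseeable: the protocol has a rule for positive arrivals, eligibility requires at least 5 drinking days in the past 30, and Session 2 follows two weeks of ordinary drinking.

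Residual TAC would enter one side of the comparison only. It can raise AUC and, less so, peak. It can shift the TAC-BrAC peak difference in the Bland-Altman analysis and shorten the estimated delay to the TAC peak. It can also obscure the rise after the first beer, on which H1a turns. Because it may be present in one session and not the other, it can add noise to the H1c correlation that has nothing to do with the monitor's repeatability.

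**Working it through.** The documents state no lag, washout time or residual TAC, so there is no figure to reproduce. What follows is an illustration.

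**From the documents:** three 12 oz beers at about 4.5% ABV, each drunk in 15 minutes and followed by a 15-minute break; example detection level 0.02 g/dL; arrival limit for waiting 0.02%; 40 completers.

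**Assumed, not from the documents:** TAC on the same scale as BrAC; first-order lag, τ·dTAC/dt = BrAC − TAC, with τ of 0.5, 1 or 2 h; elimination β of 0.010, 0.015 or 0.020 g/dL per hour; earlier drinking with BrAC falling from 0.08 to zero; a gap of 0.5, 1 or 1.5 h between zero breath and the first beer; 75 kg; distribution volume 0.6 L/kg; absorption 4 per hour; AUC over 8 h from the first beer.

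**Dose.** 355 mL × 0.045 × 0.789 = 12.6 g ethanol per beer.

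**TAC when breath reaches zero.** T0 = βτ·(1 − exp(−0.08/(βτ))).
- β 0.015, τ 1 h: 0.015 × (1 − exp(−5.33)) = 0.0149.
- β 0.020, τ 2 h: 0.040 × (1 − exp(−2)) = 0.0346.

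**TAC at the first beer.** T1 = T0·exp(−gap/τ).
- β 0.015, τ 1 h, gap 1 h: 0.0149 × exp(−1) = 0.0055.
- β 0.020, τ 2 h, gap 0.5 h: 0.0346 × exp(−0.25) = 0.0269.

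**Session with earlier drinking against a clean start** (ranges over β and gap, TAC in g/dL):

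| τ | T0 | T1 | 3-beer peak | AUC | Rise in first 30 min: clean | Rise in first 30 min: after drinking |
|---|---|---|---|---|---|---|
| 0.5 h | 0.005 to 0.010 | 0.0002 to 0.0037 | 0.0% to +0.1% | 0.0% to +1.7% | 0.0045 to 0.0061 | 0.0030 to 0.0060 |
| 1 h | 0.010 to 0.0196 | 0.0022 to 0.0119 | +0.2% to +2.9% | +0.8% to +11.4% | 0.0025 to 0.0035 | 0.0002 to 0.0028 |
| 2 h | 0.0196 to 0.0346 | 0.0093 to 0.0269 | +2.9% to +26.4% | +7.7% to +53.5% | 0.0014 to 0.0019 | 0.0000 to 0.0006 |

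**TAC-BrAC peak difference.** BrAC is unchanged, so the difference moves by the change in TAC peak. At 1 h this is 0.0001 (0.0523 to 0.0524) to 0.0009 (0.0341 to 0.0350). At 2 h it is 0.0012 (0.0432 to 0.0444) to 0.0067 (0.0255 to 0.0322).

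**Time to TAC peak.** At 2 h it comes earlier by 0.13 h (4.08 to 3.95) to 0.34 h (2.94 to 2.60). At 1 h the shift is at most 0.05 h (2.50 to 2.45).

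**Detection.** T1 reaches 0.02 in 3 of the 27 combinations, all at τ 2 h with β of at least 0.015 and a gap of 1 h or less. In those three the first 30 minutes show no rise to four decimals, so the slope rule would not be met. A clean first beer also stays below 0.02 within its 30 minutes in this model (0.0061 at most). The model therefore shows how much of the rise is hidden, not how many calls would change. With 40 participants, 60% is 24, and each wrong call moves the rate by 1/40 = 2.5 points (1/20 = 5 points with 20).

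**Weight of one session.** If clean AUCs are similar, one affected session among 40 moves the mean AUC by at most 53.5%/40 = 1.3%.

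**Subtracting a constant baseline.** In the worst 1 h case the raw peak is 0.0350 against a clean 0.0341 (+2.9%). Subtracting T1 gives 0.0350 − 0.0119 = 0.0231 (−32%). For a falling start, subtraction over-corrects.

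**The case against.** The strongest reply is that drinking does not begin when breath clears. The protocol lets the participant join the appointment at that point. In Session 1, device training, vital signs, urine tests, a snack and questionnaires come before the first beer; in Session 2 a survey replaces the training. TAC decays meanwhile. This stands, and the gap in the working allows for it, but the duration is not stated and may differ between sessions.

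Second, detection needs a visible rise and fall as well as a level. This also stands. A reader might infer that leftover TAC could pass as detection of the first beer, but a falling curve does not supply the required rise.

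Third, an elevated start may be visible, because recording begins at pairing, and before Session 2 there are field readings and morning reports of drinking. This stands in part: the plan does not say that the monitor is on the wrist during the preparatory steps, or that anyone uses those readings.

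Fourth, AUC, the most sensitive measure, is not used in H1c or in the H1b2 peak comparisons. That is correct, and the effect on H1c has not been quantified.

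Finally, the size rests on outside assumptions. It does. But the delay is something the study sets out to measure, so the plan cannot presume that it is short.

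**Conclusion.** The gap is real and of limited, conditional size. Zero BrAC is the only alcohol condition for either session, TAC is expected to trail it, and the TAC measures have no baseline. A session after recent drinking can therefore carry TAC that BrAC does not show. Under the assumed model the effect is negligible at a 0.5 h lag, small to moderate at 1 h and material at 2 h, more for AUC and the one-beer reading than for the three-beer peak. The share of sessions affected is unknown. Drinking the night before matters only if breath cleared shortly before the session.

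Three stronger readings are not supported:
- **That the TAC baseline, peak, AUC and detection results are corrupted generally.** Only sessions preceded by recent drinking are at risk, and a short lag leaves even those almost unchanged.
- **That the 0.02% arrival limit caps residual TAC at 0.02 g/dL.** TAC reflects BrAC from before arrival. At 0.020 per hour, BrAC two hours before zero was 0.04, and the model gives 0.0346 when breath clears.
- **That TAC should gate entry.** This would let the unvalidated device choose its own validation sessions, and it would set a new rule for when alcohol is given. The documents do not define a zero level for the device either.

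**What to change.** Change the analysis and the recording, and leave entry and dosing rules alone.

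1. In both sessions, have the Skyn worn and recording during the existing pre-drink steps. Define a fixed window, for example the last 15 to 30 minutes before the first beer, as the TAC baseline.
2. Compute peak and AUC, and apply the 0.02 g/dL level, as the rise above that baseline. Report the raw values beside them.
3. Flag every session with a positive arrival BrAC, or with pre-drink TAC that is non-zero or falling. Report how many there are in each session.
4. Repeat H1a, H1b and H1c without the flagged sessions.

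The cost is a few sentences in the plan, some extra analysis and no new equipment. Subtraction suits a steady offset but over-corrects a falling curve, as the working shows. Where flagged sessions have falling TAC, the analysis without them is therefore the one to rely on. It has a slightly smaller n, and for H1c each flagged session removes a pair.

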Transdermal alcohol monitors can provide noninvasive, continuous monitoring of alcohol use by detecting ethanol diffused through the skin.^{27,31} Secure Continuous Remote Alcohol Monitor (SCRAM) anklet (Alcohol Monitoring Systems, Inc.) is the most widely used transdermal monitor but is designed to be used for law enforcement purposes.³² However, wider application of SCRAM anklet in clinical and intervention settings is limited by its shortcomings including its large size, high cost, and social stigma.^{20,25,29} The newest generation of wrist-worn alcohol monitor (BACtrack Skyn) is designed for consumer use and

addresses these limitations. The device looks like a fitness tracker, is inexpensive, samples up to every second, and transmits and shows data in real-time via a smartphone app. These advantages make this wrist-worn alcohol monitor a potentially ideal tool to be incorporated into smartphone-based intervention for alcohol use. However, prior to its application in research, thorough validation investigations of the monitor are needed. In this project, we will validate the Skyn monitor among 20 HIV+ drinkers and 20 HIV- drinkers (as comparison group) in both laboratory and field settings.

Fig.1. BACtrack Skyn Alcohol Monitor

5. Specific Aims:

Aim 1: Assess the validity and reliability of the Skyn monitor through comparison with laboratory grade breathalyzer in two fixed-dose lab alcohol administration sessions (Sec. 4.3, 4.5)

Hypothesis 1a: The monitor will be able to detect alcohol use at a low threshold (e.g., one drink).

Hypothesis 1b: The parameters of transdermal alcohol concentration (TAC) (e.g., peak, time-to-peak, area under the curve) will be correlated with number of drinks and breath alcohol concentration (BrAC).

Hypothesis 1c: The TAC readings in two lab sessions will show high correlation (test-retest reliability).

Aim 2: Validate Skyn monitor in daily life using a 2-week ecological momentary assessment (EMA), and evaluate its acceptability and usability for daily alcohol monitoring (Sec.4.4)

Hypothesis 2a: The monitor detected drinking episodes will correspond with self-reports in EMA.

Hypothesis 2b: The TAC readings will correlate with number of drinks in each drinking episode.

Exploratory Aim: Explore factors (e.g., gender, HIV status) that may be associated with individual differences in monitor readings (e.g., peak, time-to-peak, correlation with consumption level).

6. Research Plan:

Overview

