At the end of the 90-minute drinking period, participants will give breath alcohol readings approximately every 15 minutes for the remainder of the session. Every hour participants will also complete the same brief packet of questionnaires they completed earlier in the session. At the end of the evening participants will remove the SCRAM anklet. All participants are required to remain in the simulated lab or research office for two hours after drinking and until the participant's breath alcohol drops to the safe level of 0.00%. During this time, participants will be provided free Wi-Fi, TV, magazines, snacks and nonalcoholic beverages (e.g., water, juice).

Once the participant's breath alcohol level falls to a BrAC of 0.00%, they will be provided transportation back home. This transportation can only be taken directly home. Transportation will be by car unless the participant resides within a half mile of the research facility, in which case there will be an option for them to walk, along with a member of the study staff. For the participant's safety, it will not be possible for them to drive themselves home or for them to have a friend or family member pick them up.

The whole lab session is expected to last about 5-6 hours, and participants will receive \$15/hour. Payment for drinking session is capped at \$90 as we expect most people will reach .00% by then. Participants who come to their lab session as originally scheduled will be provided an additional \$10 payment.

Field Test. After Lab Session 1 or when “field test only” participants come to the lab to pick up the device, participants will be instructed to wear the Skyn monitor in their daily life for a 2-week period. They can see the readings from the Skyn app on their phone if they want, but not required for this study. They will be allowed to take it off for shower or bath, swimming, charging the device, or when their activities may cause damage to the monitor (e.g., exposure in the rain). Since the monitor also has a temperature sensor, it’s possible to determine whether participants take it off. We will ask participants to check the battery status every other day and charge it if needed. The RA will be available to answer questions over the phone to help troubleshoot remotely, or have the participant bring in the Skyn monitor if they really need in-person assistance with the device itself or the app.

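### Participants may see the Skyn readings before giving the EMA self-report that is the only field reference, so the reference can depend on the device and agreement can be inflated by an unknown amount

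*Combined protocol and SAP*

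**What the plan says.** **Access to readings.** The Background section describes a device that "transmits and shows data in real-time via a smartphone app". Under Lab Session 1, "The RA will also help download the Skyn app and show participants how to pair the app with the monitor". The Field Test section then says of participants: "They can see the readings from the Skyn app on their phone if they want, but not required for this study".

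**The reference.** Hypothesis 2a reads "The monitor detected drinking episodes will correspond with self-reports in EMA". The analysis plan for Aim 2 computes detection rates by self-reported number of drinks, with an ROC curve (H2a). It relates peak TAC and AUC to self-reported drinks, first by simple correlation and then by a multilevel model (H2b). No breath test or other objective measure of drinking is planned in the field.

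**How self-report is collected.** The EMA section sets up two channels. In the first, "participants will be asked to initiate an on-demand survey in the app whenever they start a drinking episode"; that survey also asks for amounts and ending times. In the second, "the EMA app will also prompt questions at a fixed schedule every morning to ask about alcohol consumption in the past 24 hours", with the stated purpose "To capture any potentially missed self-initiated entry at the time of drinking". In addition, "The morning prompts will also include reminders to check the battery life of the monitor".

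**What is not stated.** The documents give no rule on the order of viewing and reporting, no record of viewing, no separate analysis of the two channels and no related sensitivity analysis.

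**The concern.** A validation study needs a reference obtained without knowledge of the index test. Here the person supplying the reference may look at the index test first. A rise on the screen could prompt a report that would otherwise have been missed. The absence of a rise could leave an episode unreported, and a reported amount could drift towards what the reading suggests. Each of these moves the report towards the device, which is the direction of H2a and H2b. The morning prompt is the most exposed part, because it exists to recover episodes not entered at the time. At stake is whether field agreement can be read as evidence about the monitor alone. Aim 1 is not affected, since its reference is BrAC and observed beers.

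**Working it through.** The plan gives no figure for this effect. Its Aim 2 power statement neither depends on it nor is disputed here. What follows shows direction and plausible size under assumptions.

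**1. Forgotten episodes prompted by viewing**

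Inputs:
- 100 true episodes, for scale.
- Detection rate 60%. This borrows the H1a threshold as a convenient value; the plan sets no pass mark for H2a.
- 20% of episodes forgotten without a cue, independently of detection (assumed).
- A share q of the detected-but-forgotten episodes prompted by viewing (assumed).

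Reported without viewing: 80, of which 0.60 × 80 = 48 are detected. Detected but forgotten: 0.60 × 20 = 12.

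Apparent detection = (48 + 12q) / (80 + 12q)

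| q | Calculation | Apparent detection |
|---|---|---|
| 0 | 48/80 | 60.0% |
| 0.25 | 51/83 | 61.4% |
| 0.5 | 54/86 | 62.8% |
| 1 | 60/92 | 65.2% |

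At q = 1, with 10% forgotten the result is 60/(90 + 6) = 62.5%, and with 30% forgotten it is 60/(70 + 18) = 68.2%. True detection is 60% throughout.

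**2. Reports moved in both directions**

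The first calculation ignores false detections and ignores episodes left unreported because the device showed nothing. To include both, assume drinking on 5/30 of days (the minimum in the inclusion criteria), detection 0.60, a device false-positive rate of 0.05, 10% of drinking days omitted from the report, and no over-reporting. The joint proportions of days are:

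- device+, report+: (1/6)(0.6)(0.9) = 0.0900
- device+, report−: (1/6)(0.6)(0.1) + (5/6)(0.05) = 0.0517
- device−, report+: (1/6)(0.4)(0.9) = 0.0600

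If a share c of both discordant cells moves to agree with the device:

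Apparent sensitivity = (0.0900 + 0.0517c) / (0.0900 + 0.0517c + 0.0600(1 − c))

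This gives 0.600, 0.638, 0.696 and 0.794 at c = 0, 0.10, 0.25 and 0.50. If only the device+, report− days move, c = 0.50 gives 0.1158/0.1758 = 0.659. The documents support no particular value of c.

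**3. H2b**

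Suppose the reported amount is (1 − w) × own recall + w × the amount implied by the device, both standardised, with true correlation r. Then

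r* = [(1 − w)r + w] / √[(1 − w)² + w² + 2w(1 − w)r]

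For r = 0.60, r* is 0.64/√0.928 = 0.66 at w = 0.10 and 0.70/√0.85 = 0.76 at w = 0.25. The weights are assumed.

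**4. Where exposure lies**

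An on-demand entry is opened when drinking starts, and the H1b2 analysis anticipates that the TAC peak comes after the BrAC peak. The fact of an episode entered this way will mostly precede a readable rise. Amounts and ending times cannot be known at the start, so they remain exposed even in this channel. Morning-recalled episodes are exposed in full.

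**The case against.** **Viewing is only permitted.** The documents do not say how often anyone looks. Nor do they say that the app keeps a history that would show last night's curve the next morning, or that the battery check opens the screen with the readings. A reader might infer that agreement is inflated; the documents support only that it can be. This stands.

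**The plan already allows a partial check.** A reader might infer that nothing collected bears on the size of the effect. That goes too far, because the two channels are separate surveys. In the first calculation the prompted episodes would all be detected (12/12), against 60% elsewhere, and a comparison by channel could reveal this. The check is imperfect, since episodes forgotten at the time may differ in other ways, and the comparison is not planned.

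**A more dramatic figure is not relevant.** In the same illustration the share of detections backed by a report goes from 48/60 = 80% to 60/60 = 100%. H2a does not list that measure. With no false detections assumed, the true share is already 100%, so viewing there corrects an understatement.

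**The direction for H2b is not certain.** Viewing might change drinking itself. If it narrowed the spread of drinks to 0.75 of its SD, a correlation of 0.60 would fall to 0.45/√(0.64 + 0.2025) = 0.49. That is a separate effect and does not make the reference independent.

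**Usability is an Aim 2 outcome, so the app should stay available.** Agreed. Fixing the order of reporting and viewing does not require hiding it.

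**Conclusion.** The concern holds as a limited design finding. The only reference for H2a and H2b may be given after the participant has seen the device readings, and nothing in the plan protects or documents its independence. Field agreement can be inflated, mainly through morning-recalled episodes and late-entered amounts or end times.

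The size cannot be computed from the documents. With 60% detection and 20% forgetting, both assumed, prompting alone moves apparent detection to 61–65%. The top of that range requires every detected-but-forgotten episode to be prompted. Larger shifts need reports to move in both directions, for which the documents give no rate.

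Aim 2 remains analysable, and this is a cheap improvement. It does not show that the field results are invalid.

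**What to change.** 1. Keep the Skyn app available. Instruct participants to complete the morning drinking questions before opening it that day.
2. Place one yes/no item after those questions, asking whether readings were viewed since the last prompt.
3. Report H2a and H2b separately for on-demand and morning-only entries. Classify them by entry channel and by time relative to the self-reported start of drinking.
4. Present results by viewing status descriptively only, because viewing may follow drinking.

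Entries should not be selected by whether TAC had already risen, tempting as that is, because it selects on the device result. Undetected episodes have no rise and all stay in, while detected episodes entered late drop out. With 60 detected and 40 undetected episodes and 20% of the detected ones entered late (assumed), detection becomes 48/(48 + 40) = 54.5% instead of 60%.

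**Cost.** One instruction and one EMA item per day; sample size and visits do not change. The burden is slight, viewing is self-reported, the item may itself prompt viewing, and morning-only entries may be few. If data collection is already advanced, step 3 can still be done provided the channel and time of each entry were kept.
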